7.2 Exclusion Criteria

Subjects will be excluded from participation in this study if they meet any of the following exclusion criteria:

- 1. Subject has Type 2 or 3 Gaucher disease, has severe neurological signs and symptoms, defined as complete ocular paralysis, overt myoclonus or history of seizures, characteristic of neuronopathic Gaucher disease, or has a tremor, peripheral neuropathy or symptoms of Parkinson's disease.
- 2. Subject has any one of the following:
 - a. Hemoglobin value < 9.0 g/dL, or
 - b. Platelet count $< 70 \times 10^9/L$, or
 - c. Spleen volume $> 10 \times \text{normal}$, or
 - d. Pulmonary hypertension
- 3. Subject has experienced a prior anaphylactic or anaphylactoid reaction (of any severity) to ERT.
- 4. Treatment-naïve subject has history of clinically significant (CS) anti-GCase antibodies.
- 5. Subject has a contraindication to ERT, in the opinion of the Investigator.
- 6. Subject has a contraindication to HSC transplantation, in the opinion of the Investigator.
- 7. Subject presents with iron, folic acid, and/or vitamin B12 deficiency sustained anemia during Screening.
- 8. Subject has idiopathic thrombocytopenic purpura (ITP), thrombotic thrombocytopenic purpura (TTP), thrombocytopenia, anemia, hepatomegaly, splenomegaly, and/or osteoporosis unrelated to Gaucher disease, in the opinion of the Investigator.
- 9. Subject has a clinical co-morbidity such as neurologic, cardiovascular, pulmonary, hepatic, gastrointestinal, renal, hematologic, endocrine, metabolic, genetic, immunologic, neoplastic, or psychiatric disease, other medical condition(s), or intercurrent illnesses that may confound the study results or, in the opinion of the Investigator, may preclude participation in the study.
- 10. Subject is a pregnant and/or lactating female.
- 11. Subject is unable to understand the nature, scope, and possible consequences of the study.
- 12. Subject has diabetes mellitus (Type 1 or Type 2).
- 13. Subject has active, progressive bone necrosis.
- 14. Subject has an active chronic infection during the Screening, Baseline, or Pre-gene Therapy Infusion Period of the study.
- 15. Subject has an active uncontrolled acute bacterial, viral, fungal, parasitic, or prion-associated infection during the Screening, Baseline, or Pre-gene Therapy Infusion Period of the study.
- 16. Subject has a history of (or current) tuberculosis.
- 17. Subject tests positive for hepatitis B virus (HBV), hepatitis C virus (HCV), human immunodeficiency virus (HIV, Type 1 or 2), human T-cell lymphotropic virus (HTLV)-1, HTLV-2, and/or syphilis on Venereal Disease Research Laboratory (VDRL) test, chemiluminescent microplate immunoassay (CMIA), or enzyme immunosorbent assay (EIA) at Screening.

- 18. Subject has a prior history of (or current) cancer or precancerous lesion or has a known genetic predisposition to cancer. The one exception is a prior history of resected squamous cell carcinoma.
- 19. Subject has any other medical condition that predisposes him/her to (or conveys increased risk of) malignancy, in the opinion of the Investigator, including history of (or current) monoclonal gammopathy of undetermined significance (MGUS).
- 20. Subject has a history of alcohol or illicit drug abuse, according to the Investigator's judgment.
- 21. Subject has undergone, or is scheduled to undergo, BMT, HSC, and/or solid organ transplant. NOTE: Subjects who are otherwise eligible for the study but are scheduled for bone marrow or HSC transplant to treat Type 1 Gaucher disease may be enrolled in the study (instead of receiving an allogeneic transplant) and undergo gene therapy infusion with AVR-RD-02.
- 22. Subject has white blood cell (WBC) count $< 3.0 \times 10^9$ /L and/or uncorrected bleeding disorder from enrollment (ie, signing of informed consent at Screening) through the Gene Therapy Infusion Period of the study (ie, the day of AVR-RD-02 gene therapy infusion).
- 23. Subject has CS immunosuppressive disease or condition, in the opinion of the Investigator, at Screening.
- 24. Subject is on (or requires treatment with) cytotoxic or immunosuppressive agents from 60 days prior to signing informed consent at Screening (ie, study enrollment) through the Week 52 study visit; the one exception is treatment with cytotoxic or immunosuppressive agents required per protocol for stem cell transplant.
- 25. Subject is on (or requires treatment with) red blood cell (RBC) growth factor (eg, erythropoietin) from 6 months prior to enrollment (ie, signing of informed consent at Screening) through the Week 52 study visit.
- 26. Subject has any condition that makes it impossible to perform MRI studies.
- 27. Subject has medical condition(s) and/or is receiving medication(s) that would contraindicate ability to undergo mobilization (including contraindication to G-CSF and/or plerixafor), apheresis, or conditioning.
- 28. Busulfan is contraindicated for the subject.
- 29. Subject has previously received treatment with AVR-RD-02 or any other gene therapy.
- 30. Subject is participating in (or plans to participate in) any other investigational drug trial, or plans to be exposed to any other investigational agent, device, and/or procedure, from 30 days prior to enrollment (ie, signing of informed consent at Screening) through study completion.

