- 22. Subject has white blood cell count (WBC) < 3.0 × 10⁹/L and/or uncorrected bleeding disorder from enrollment (ie, signing of informed consent at Screening) through the Gene Therapy Infusion Period of the study (ie, the day of AVR-RD-02 gene therapy infusion).
- Subject has CS immunosuppressive disease or condition, in the opinion of the Investigator, at Screening.
- 24. Subject is on (or requires treatment with) cytotoxic or immunosuppressive agents from 60 days prior to signing informed consent at Screening (ie, study enrollment) through the Week 52 study visit; the one exception is treatment with cytotoxic or immunosuppressive agents required per protocol for stem cell transplant.
- 25. Subject is on (or requires treatment with) red blood cell (RBC) growth factor (eg, erythropoietin) from 6 months prior to enrollment (ie, signing of informed consent at Screening) through the Week 52 study visit.
- 26. Subject has any condition that makes it impossible to perform MRI studies.
- 27. Subject has medical condition(s) and/or is receiving medication(s) that would contraindicate ability to undergo mobilization (including contraindication to granulocyte-colony stimulating factor [G-CSF] and/or plerixafor), apheresis, or conditioning.
- 28. Busulfan is contraindicated for the subject.
- 29. Subject has previously received treatment with AVR-RD-02 or any other gene therapy.
- 30. Subject is participating in (or plans to participate in) any other investigational drug trial, or plans to be exposed to any other investigational agent, device and/or procedure, from 30 days prior to enrollment (ie, signing of informed consent at Screening) through study completion.

Investigational Product, Dosage, and Mode of Administration:

Subjects will receive a single intravenous (IV) gene therapy infusion of between 3×10^6 /kg and 10×10^6 /kg body weight autologous CD34+ cell-enriched population that contains autologous CD34+ enriched HSCs that have been genetically modified *ex vivo* with an LV containing an RNA transcript that, after reverse transcription, results in codon-optimized cDNA that, upon its integration into the human genome, encodes for functional human GCase.

Endpoints:

Primary

Primary endpoints include the following:

Safety endpoints:

- Incidence and severity of AEs, incidence of serious AEs (SAEs), and incidence and severity of AEs of
 interest, including drug-product related AEs, infections, and malignancy

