Busulfan crosses the blood-brain barrier and can cause neurotoxicity, including seizures, when administered at higher doses. Therefore, anticonvulsant medication is routinely prescribed for patients undergoing myeloablative therapy with busulfan in preparation for bone marrow transplant (BMT) or hematopoietic cell transplant (HCT). Consistent with this practice, anticonvulsant prophylaxis will be administered concurrent with busulfan administration for conditioning in this study. Levetiracetam will be administered in this study as described in Section 8.1.1.3. The dosing regimen selected for levetiracetam has been shown in literature to be effective at preventing seizures in adults receiving conditioning with busulfan in preparation for HSCT, and to have an acceptable safety profile when administered in combination with busulfan (Akiyama 2018). For subjects with contraindications to levetiracetam, an alternative anti-

convulsant medication (eg, benzodiazepines or valproic acid) may be used before and after busulfan treatment (Busulfan PI).

Busulfan treatment at the approved dose and schedule produces profound, transient myelosuppression in all patients. Hematologic changes have been observed in subjects receiving myeloablative busulfan conditioning regimens used in other autologous LV-mediated gene therapy studies for TDT, sickle cell disease (SCD), metachromatic leukodystrophy (MLD), leukocytes adhesion deficiency-1, and X-linked chronic granulomatous disease (Fumagalli 2022; Sessa 2016; Thompson 2018; Tisdale 2018; Kohn 2020; see also the Investigator's Brochure for AVR-RD-02). Similar outcomes were achieved by Mamcarz et al in LV-mediated gene therapy for X-linked severe combined immunodeficiency (SCID-X1) patients, albeit targeted busulfan was indicated at low dose (Mamcarz 2019).

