8.1.1.3 Conditioning

After the site receives the investigational product dispositioned for clinical use, the subject will enter the Conditioning phase.

During this phase of the study, subjects will receive a QD, 4-day myeloablative conditioning regimen of IV busulfan that is informed by a weight-based test dose of 0.8 mg/kg administered on Conditioning Day -6. The test dose will serve to establish the predicted PK for each individual subject, as part of the TDM. The test dose of busulfan will be administered on Conditioning Day -6 for sites using LC-MS to perform busulfan TDM and on Conditioning Day -5 for sites using the immunoassay kit to perform busulfan TDM.

For Conditioning Days -4, -3, -2, and -1, a dose simulation program will be used to determine the busulfan dose required for each subject to achieve the busulfan target AUC, as described in the Study Treatment Manual. The myeloablative cumulative target for busulfan exposure in the AVRO-RD-02-201 study will be an AUC of $90_{\text{(day 0-4)}} \pm 2\%$ mg•hr/L.

Once-daily dosing of IV busulfan with TDM will be administered as follows for sites using LC-MS to perform TDM (also see Table 1):

- On Conditioning Days -4 and -3, a PK- and weight-based guided IV busulfan dose, based on TDM PK of the test dose on Day -6 and the respective calculated AUC generated from the web-based dose simulation program, will be administered.
- For Conditioning Day -2, the dose simulation program will be used to determine the busulfan dose required for each subject to achieve the busulfan target AUC based on TDM PK of the test dose and Day -4.
- For Conditioning Day -1, the dose simulation program will be used to determine the busulfan dose required for each subject to achieve the busulfan target AUC based on TDM PK of the test dose, Day -4, and Day -3.
- If AUC of the previous dose is outside of the AUC_{target} determined by the web-based dose simulation program, the busulfan dose will be adjusted accordingly.

Table 1: PK- and Weight-Based Guided Busulfan Conditioning Regimen for Sites Using LC-MS to Perform Busulfan TDM

Dosing Day	Busulfan Dose (mg/kg/day)	TDM PK Schedule for Busulfan Dose Determination
Day -6	Test dose of 0.8 mg/kg	PK sampling at 1, 3, 5, and 7 hours post dose; TDM PK results will be used to inform the dose on Day -4 and Day -3

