Day -4	Dose based on TDM PK of test dose	PK sampling at 1, 3, and 5 hours post dose; TDM PK results will be used to inform the dose on Day -3 together with TDM PK results from the test dose
Day -3	Dose based on TDM PK of test dose and Day -4	PK sampling at 1, 3, and 5 hours post dose; TDM PK results will be used to inform the dose on Day -2 together with TDM PK results from the test dose and Day -4
Day -2	Dose based on TDM PK of test dose, Day -4, and Day -3	PK sampling at 1, 3, and 5 hours post dose; TDM PK results will be used to inform the dose on Day -1 together with TDM PK results from the test dose, Day -4, and Day -3
Day -1	Dose based on TDM PK of test dose, Day -4, Day -3, and Day -2	PK sampling at 1, 3, and 5 hours post dose; TDM PK results will be used to inform the cumulative AUC

Abbreviations: AUC = area-under-the curve; PK = pharmacokinetics; TDM = therapeutic drug monitoring.

Pharmacokinetic sampling may also be performed on Day -5 to support optimization of busulfan exposure.

Anticonvulsant medication will be administered for seizure prophylaxis in conjunction with busulfan administration. Levetiracetam will be administered at a dose of 1,000 mg per day from Conditioning Day -8 (ie, 2 days before administration of the busulfan test dose) until 1 day after the administration of the 4-day busulfan conditioning regimen. For subjects with contraindication to levetiracetam, an alternative anticonvulsant medication (eg, benzodiazepines or valproic acid) may be used.

After the 4-day conditioning regimen is administered, a busulfan washout period after the end of the last busulfan infusion for a minimum of 24 hours and up to a maximum of 48 hours is required prior to AVR-RD-02 administration.

Timing for the conditioning procedures is outlined in the Schedule of Assessments in Table 5, with further information included in the Study Treatment Manual.

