8.1.2 Gene Therapy Infusion Period (1 Day)

After completion of the busulfan washout period (ie, a minimum of 24 hours up to a maximum of 48 hours after the end of the last busulfan infusion), AVR-RD-02 will be administered once by IV infusion. Prior to IV infusion, subject identifiers on AVR-RD-02 investigational product must be checked against the intended recipient, and the investigational product must be thawed at 37°C prior to use. Further details on the gene therapy infusion process may be found in the Study Treatment Manual.

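### Exclusion criterion 22 keeps the WBC limit in force through infusion day with no exception for busulfan, so it conflicts with Section 8.1.2 for any subject who falls below 3.0 × 10⁹/L before infusion

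*Protocol*

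**What the plan says.** Section 7.2 opens with "Subjects will be excluded from participation in this study if they meet any of the following exclusion criteria". Criterion 22 then names two conditions joined by and/or: WBC below 3.0 × 10⁹/L, and "uncorrected bleeding disorder from enrollment (ie, signing of informed consent at Screening) through the Gene Therapy Infusion Period of the study". The synopsis gives the same end point, "through the Gene Therapy Infusion Period of the study (ie, the day of AVR-RD-02 gene therapy infusion". Neither place mentions conditioning.

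Two criteria later, criterion 24 bars cytotoxic and immunosuppressive agents through Week 52 but adds that "the one exception is treatment with cytotoxic or immunosuppressive agents required per protocol for stem cell transplant".

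Section 6.2.2.2 says that busulfan at the approved dose and schedule "produces profound, transient myelosuppression in all patients". Under Section 8.1.1.3 the test dose is "administered on Conditioning Day -6 for sites using LC-MS to perform busulfan TDM and on Conditioning Day -5 for sites" using the immunoassay kit, and the myeloablative doses follow on Days -4 to -1. A washout "for a minimum of 24 hours and up to a maximum of 48 hours is required prior to AVR-RD-02 administration". Section 8.1.2 then states that, after the washout, "AVR-RD-02 will be administered once by IV infusion". It sets checks on subject identity and thawing, but none on WBC.

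**The concern.** An eligibility limit on a blood count normally stops before the treatment that is meant to lower that count. This one does not. Criterion 24 shows that the drafters wrote an exception where they saw an eligibility rule overlap with conditioning; criterion 22 has none.

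What is at stake is a patient-protection instruction, not an estimate. Followed literally, criterion 22 would exclude from infusion a subject who has already received myeloablative busulfan. Section 7 does not permit waivers, and Section 7.4.1 asks for the enrollment criteria to be followed explicitly, so the protocol gives a site no sanctioned way to set the criterion aside.

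**Working it through.** There is no plan figure to reproduce: the sample size was chosen without statistical considerations and no hypothesis test is planned. The check is to lay the rules on one timeline and count.

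| Labelled day | Protocol action (8.1.1.3, 8.1.2) | CBC in Table 5 | Criterion 22 WBC limit, natural reading |
|---|---|---|---|
| -7 | before any busulfan | yes | in force |
| -6 | test dose, LC-MS sites | no | in force |
| -5 | test dose, immunoassay sites | no | in force |
| -4 | busulfan dose 1 | no | in force |
| -3, -2, -1 | busulfan doses 2 to 4 | yes, each day | in force |
| washout, 24 to 48 hours | none | yes, daily | in force |
| 0 | infusion | yes, drawn before infusion | in force (last day) |

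**Length of overlap.** Labelled days from the test dose to Day 0, counting both ends:
- LC-MS sites: 0 − (−6) + 1 = 7 days.
- Immunoassay sites: 0 − (−5) + 1 = 6 days.

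**Would a fall be seen?** Scheduled counts in the overlap are Days -3, -2, -1 and 0, which makes 4. The daily washout samples add 0 to 2, depending on whether they are separate from the Day -1 and Day 0 samples. The total is 4 to 6 per subject. The Table 5 footnotes include WBC in the CBC and place the Day 0 sample before infusion, so a value below 3.0 would be on record before infusion.

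**Which rule would then apply?** Criterion 22 says the subject is excluded. Section 8.1.2 says infuse. Criterion 24 does not settle it, because its exception covers receiving an agent, not the laboratory result that follows.

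**How many subjects?** This cannot be derived. Section 6.2.2.2 gives the size and universality of myelosuppression but not its timing. Section 7.4.5 looks for ANC recovery to 0.5 × 10⁹/L by Day 42, which shows that low counts are expected after infusion but not where they stand on Day 0. The range is none to all of those conditioned (8 to 16 subjects were planned in total).

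**What would be lost by ending the limit at Day -7?** CBCs before busulfan: Table 4 has Screening 1 + Baseline 1 + Mobilization 4 + Apheresis 2 = 8. Table 5 adds Day -7, giving 9. All 9 are kept. Day -7 is one day before the test dose at LC-MS sites and two days before it at immunoassay sites.

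**The case against.** **Eligibility is settled at entry.** Section 6.1 has eligibility confirmed before the Baseline Period, and Section 8.1.1.1 starts mobilization in subjects who meet the criteria. This narrows the conflict but does not remove it. Other criteria are tied to Screening or end with the Pre-gene Therapy Infusion Period, whereas criterion 22 expressly runs to infusion day.

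**The window may attach only to the bleeding disorder.** This is grammatically possible. The WBC limit would then be undated, like the hemoglobin and platelet limits in criterion 2, and the conflict with Section 8.1.2 would not be established. The natural reading covers both conditions joined by and/or, and the edit removes the ambiguity on either reading.

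**Nothing forces withdrawal.** A reader might infer that Section 7.4.1 would oblige the site to discontinue a subject with low counts and withhold the cells. It does not clearly say that. Its mandatory sentence concerns subjects inadvertently enrolled without meeting entry criteria, and it leaves withdrawal for a clinically significant laboratory value to the investigator. Sites would very probably infuse. That part of the objection stands, but it relies on sites disregarding a written exclusion after myeloablation has begun.

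**Little remains to fix.** The SAP Introduction states that the study was prematurely discontinued. This stands, and it limits the practical reach of the edit.

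**Conclusion.** The conflict is real but conditional. It rests on the natural reading of criterion 22 and arises only for a subject whose WBC is below 3.0 × 10⁹/L after busulfan starts and before infusion. The window in which that can happen is 7 or 6 labelled days, depending on the assay used at the site. The number of subjects is undetermined.

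Three stronger conclusions are tempting and are not supported:
- *Every conditioned subject would breach the criterion.* No section gives the day on which WBC crosses 3.0.
- *The listings would fill with spurious eligibility deviations.* SAP Section 8.2 lists all deviations, but their identification and classification sit in a Protocol Deviation Management Plan that is not among the documents.
- *The protocol elsewhere places a WBC check before busulfan.* Section 7.3 links the remaining exclusions to fitness for both conditioning and infusion, and Section 8.3.1 concerns product release results. Neither mentions WBC.

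No estimate changes, because the Infused population in SAP Section 5.5.3 is defined by treatment received. The gain is removal of an instruction that, followed literally, would exclude an already myeloablated subject from infusion.

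**What to change.** Reword criterion 22 in Section 7.2 and in the synopsis, in one of two ways:

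- *WBC count < 3.0 × 10⁹/L from enrollment through the Conditioning Day -7 CBC (before the busulfan test dose), and/or uncorrected bleeding disorder from enrollment through the Gene Therapy Infusion Period.*
- Keep the present window and add: *except WBC decreases resulting from protocol-required conditioning.*

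The first is cleaner because it needs no judgment about the cause of a fall. Criterion 24's exception should not be copied verbatim: it exempts a treatment and does not fit a laboratory threshold.

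The cost is one clause in two places. No new sample is needed, since the Day -7 CBC is already scheduled, and the bleeding-disorder window is unchanged. Later falls are still captured, because Section 9.2.1 records WBC counts of Grade 3 or higher as adverse events whether or not the investigator judges them clinically significant. Given the premature discontinuation, the change serves any further subject conditioned under this text.

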7.3 Rationale for Inclusion or Exclusion of Certain Study Candidates

AVR-RD-02 is an *ex vivo* LV, autologous gene therapy intended for the durable provision of functional GCase in subjects with Gaucher disease. Enrollment is restricted to subjects with Type 1 Gaucher disease for this Phase 1/2 study to reduce between-subject symptom, and thus, endpoint variability. The most robust assessment of safety and efficacy with AVR-RD-02 treatment would be generated in subjects with Type 1 Gaucher disease who are switch-stable (as defined in this protocol) and in treatment-naïve subjects with Type 1 Gaucher disease. While it is generally recognized that individuals with Types 2 and 3 Gaucher disease exhibit significant neurologic features and markedly reduced life spans, the natural history of these conditions,

along with reports of treatment response, are not well understood. Whereas clinical study data on the safety and efficacy of treatments for Types 2 and 3 Gaucher disease have not been published, there is an extensive body of literature that has arisen from the numerous clinical studies conducted in Type 1 Gaucher disease, thereby allowing for more meaningful interpretation of outcomes in comparison to previous observations (Barton 1991; Ben Turkia 2013; Cox 2012; Cox 2015; Elstein 2015; Gonzalez 2013; Grabowski 1995; Mistry 2015; Pastores 2014; Zimran 2011).

Exclusion of subjects with Types 2 and 3 Gaucher disease prevents the potential introduction of confounding safety signals (see Section 6.2). Thus:

- Inclusion criterion 3 identifies the Type 1 Gaucher disease study population; and,
- Exclusion criterion 1 eliminates subjects who have, or are suspected of having, Types 2 or 3 Gaucher disease.

The requirement that subjects be postpubertal (defined as Tanner Stage 5 genital development and pubic hair distribution in males and breast development in females) at Screening was included to ensure that subjects 18 years to 21 years of age are not continuing to undergo the metabolic and other physical changes associated with puberty. The requirement for subjects to be ≤ 50 years of age at Screening was included as rates of engraftment may decrease with increasing age (see Section 6.2). Thus:

• Inclusion criterion 2 identifies eligible subjects as ≥ 18 years and ≤ 50 years old and postpubertal, defined as Tanner Stage 5 genital development and pubic hair distribution in males and breast development in females.

As the impact of the planned conditioning regimen on infertility and primary ovarian insufficiency in this study population is not fully understood, the entry criteria include items to off-set the potential risk of infertility to female and male subjects (see Section 6.2.2):

- Inclusion criterion 4 mitigates the female infertility risk associated with this protocol by offering reproductive counseling and oocyte harvesting and cryopreservation.
- Inclusion criterion 7 prohibits male and female subjects from donating sperm or egg, respectively, after undergoing conditioning, and offers male subjects the option of sperm cryopreservation prior to conditioning.

Inclusion criteria 10 through 13 define the switch-stable subjects, and inclusion criteria 14 and 15 define the treatment-naïve subjects.

Individuals may be allowed to re-screen based on discussions with the PI and the Sponsor's medical representative or designee's review and approval.

Other exclusion criteria are related to the subjects' fitness for the conditioning regimen and gene therapy infusion. In addition, to most accurately assess the effects of AVRO-RD-201, subjects with medical conditions that can potentially confound measures of safety and efficacy will also be excluded.

